2.1 Study Procedures by Visit and Treatment Cycle

Laboratory analyses and clinical examinations are to be repeated for a total treatment duration time of 4 to 6 months. Radiologic examinations are to be performed before chemotherapy and before surgery (from randomization to disease progression or until surgery).

The maximum number of treatment cycles allowed is 4.

The sequence of events for up to 4 cycles is described below.

2.2 Screening/Baseline visit

Informed consent must be obtained before performing any study-related procedures. Screening procedures may be done up to 4 weeks prior the start of neo-adjuvant therapy. Screening evaluation will include blood work, pregnancy testing, medical history, physical exam (including tumor measurements of the breast and lymph node, height, weight, blood pressure, heart rate and temperature) electrocardiogram, and echocardiogram. Tumor measurements will be recorded as the largest dimension in centimeters. Medical history should include relevant underlying conditions and concomitant medications. Baseline signs and symptoms are to be recorded and followed throughout the trial. A mammography and ultrasound will be performed to assess disease status. Prior to initiation of neo-adjuvant therapy, a core tumor breast biopsy and blood sample will be obtained for baseline biomarkers expression studies. If a patient entered the study (i.e. signed informed consent) prior to histological confirmation of breast cancer, this biopsy may serve the dual purpose of confirming the diagnosis and obtaining tissue for biomarkers research. Following confirmation of eligibility, a blocked randomization will be used to randomize patients to either arm 1 or arm 2. A master sequence of randomization numbers for each arm will be generated.

For those study patients who voluntarily agree to have an optional serum samples taken for biomarkers expression; blood samples will be stored and the biomarkers expression will be done at later time (see lab manual). Patients will be informed that they will not be excluded from the clinical study if they do not wish to participate in the (blood samples) biomarkers study. •The biomarkers blood sample must be collected after a patient number has been obtained. (see CA163157 Procedure Manual).

• A minimum of 15 tissue slides from the tumor breast biopsy or lymph nodes (when available) will be collected at baseline and send to the central laboratory. Note: please collect all tissue slides (15 at baseline and 15 after surgery) at the site before send it out to the central lab (see lab manual)

2.2.1 Radiological Evaluation Visit

• Perform mammogram and ultrasound of the breast and nodal region to determine baseline tumor status using RECIST criteria. This radiological evaluation should be completed within 90 days before study drug administration. If more than 90 days have elapsed since the baseline radiological evaluation, the mammogram and ultrasound must be repeated before the initial infusion of study drug is administered. If, at any time, is suspected progression diseases a complete radiological evaluation must be performed.

MRI (magnetic resonance imaging), only if requested by physician).

2.3 Cycle 1 Clinic Visit

Following confirmation of eligibility, a blocked randomization will be used to randomize patients to either arm 1 or arm 2. A master sequence of randomization numbers for each arm will be generated (see CA163157 Protocol Manual). Once the subject is randomized, administration of study drug must begin within 72 hours. NOTE: If more than 72 hours have elapsed between the blood sampling for laboratory analysis and administration of ixabepilone or cetuximab, then the analyses must be repeated. (Except for cycle 1 for which baseline labs obtained within 2 weeks are accepted.)

• laboratory tests within 72 hours of beginning each cycle comprise albumin, alkaline phosphatase, ALT, AST, total bilirubin, blood urea nitrogen, calcium, chloride, creatinine, glucose, lactic dehydrogenase, magnesium (at baseline only for the ixabepilone alone arm), potassium, phosphorus, and sodium, as well as complete blood count (Hemoglobin, Hematocrit, RBC, WBC, Platelets) with differential (Neutrophils, Lymphocytes, Monocytes, Eosinophils, Basophils). CrCL "CrCl = [(140 - age) x IBW] / (Scr x 72) (x 0.85 for females)" before every cycle for patients with an abnormal creatinine.

• Laboratory tests comprise of calcium, magnesium, and potassium before every dose of cetuximab therapy (before every cycle for the ixabepilone plus cetuximab arm).

 Perform a physical examination; record weight and height, karnofsky performance scale, document vital signs. Assess signs and symptoms and document baseline adverse events.

• Subjects who are to receive ixabepilone are to be premedicated approximately 1 hour before the infusion with either 1)both an oral H1 blocker (diphenhydramine 50 mg or equivalent) and an oral H2 blocker (eg, ranitidine 150-300 mg or cimetidine 300-800 mg or nizatidine 150-300 mg or famotidine 20-40 mg); or 2) with premedication per institutional standards. Premedication with steroids is indicated in subjects who developed a hypersensitivity reaction to ixabepilone in previous cycles. Subjects who are to receive cetuximab are to be premedicated with an H₁ antagonist (e.g., 50 mg of diphenhydramine IV or

equivalent)

• Infuse ixabepilone or ixabepilone plus cetuximab accordingly with the randomization arm.

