2.0 Study Flow chart or Schedule of Events

Procedure	Screening/Baseline Visit	Prior to Each Cycle	End-of- Treatment Visit ^a	Follow-up
Eligibility Assessments				
Obtain Informed Consent	Х			
Confirm Inclusion/Exclusion Criteria Met ^b	Х			
Obtain Medical History	Х			
Safety Assessments				
Karnofsky performance scale ^{a b}	Х	Х	Х	
Record Weight and Height	Х	Х	Х	
Document Vital Signs	Х	Х	Х	
Assess Signs and Symptoms and Adverse Events $^{\rm c,o}$	Х	Х	Х	
Perform Pregnancy Test in WOCBP ^d	Х			
Perform mammogram ^e	Х		Х	
Perform ultrasound of breast and nodal region ^e	Х		Х	
(MRI)*				
Perform Laboratory Tests ^{fghi}	Х	Х	Х	Х
Prepare Paraffin Block/Slides ^j	Х		Х	
Obtain Blood Sample for biomarkers ^k **	Х		Х	
Perform Electrocardiogram	Х		Х	
Perform Echocardiogram ¹	Х			
Efficacy Assessments				
Evaluate Tumor Response RECIST Criteria ^m	Х		Х	
Clinical Drug Supplies				
Premed Before Infusion ⁿ		Х		

TMHRI Version: 8

a. Evaluate subjects who discontinue the protocol for reasons other than disease progression every 4 weeks until progression or until they receive additional anti-cancer therapy.

b. Karnofsky Performance Status of =/> 70% is required for study entry.

c. Document signs and symptoms and adverse events at least every 4 weeks until all study drug-related toxicities resolve, stabilize, return to baseline, or are deemed irreversible.

d. Pregnancy tests (serum or urine) should be performed within 72 hours of study start, or whenever pregnancy is suspected.

e. Mammogram and ultrasound should have been performed any time within 90 days prior to beginning of the study treatment and within 3 to 4 weeks of the neoadjuvant therapy completion before surgery. *MRI (magnetic resonance imaging) should be performed only if requested by the physician.

f. Laboratory tests comprise albumin, alkaline phosphatase, ALT, AST, total bilirubin, blood urea nitrogen, calcium, chloride, creatinine, glucose, lactic dehydrogenase, magnesium (at baseline only for the ixabepilone alone arm), potassium, phosphorus, and sodium, as well as complete blood count (Hemoglobin, Hematocrit, RBC, WBC, Platelets) with differential (Neutrophils, Lymphocytes, Monocytes, Eosinophils, Basophils). CrCL "CrCl = [(140 - age) x IBW] / (Scr x 72) (x 0.85 for females)" before every cycle for patients with an abnormal creatinine.

g. Perform laboratory tests within 72 hours of beginning each cycle. Perform baseline laboratory tests within four (4) weeks before administration of study drug

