h. Perform complete blood count (Hemoglobin, Hematocrit, RBC, WBC, Platelets) with differential (Neutrophils, Lymphocytes, Monocytes, Eosinophils, Basophils) at week 1 and week 2 for the first 4 cycles and thereafter at the expected time of nadir (lowest count of any type of blood cell).

i. Laboratory tests comprise of calcium, magnesium, and potassium before every dose of cetuximab therapy and for at least 8 weeks following the completion of cetuximab. Replete electrolytes as necessary.

j. Send tissue slides to the central laboratory (see lab manual). Collected at baseline, and at the time of surgery [UPTEN, EGFR and EGFR-pathway associated genes (TGF-a, CRYAB, NRAS, KRAS, AKT3, PTEN, MEK1 and KRAS amplicon genes). Additional exploratory biomarkers may include (but are not limited to) beta tubulin isoforms, ABC transporters, TACC3, HCAPG, GTSE1, Kallikreins and defined gene models associated with ixabepilone response. Tumor biomarkers will be assessed on a formalin-fixed, paraffin-embedded (TFFPET) tumor sample from a previous biopsy (baseline) and from the surgical specimen. A minimum of 15 slides will be collected at each time.

k. Serum sample for biomarkers expression at baseline, and at the time of surgery. ** Optional (Serum sample for biomarkers expression will be done at later time).
 I. A 12-lead ECG with QT measurement should be performed at screening, at the end of study/early termination, and whenever medically indicated. An Echocardiogram should be performed at screening only and whenever medically indicated.

m. Evaluate tumor response using RECIST criteria before chemotherapy and before surgery (from randomization to disease progression or until surgery).

n. Subjects who are to receive ixabepilone are to be premedicated approximately 1 hour before the infusion with both an oral H1 blocker (diphenhydramine 50 mg or equivalent) and an oral H2 blocker (eg, ranitidine 150-300 mg or cimetidine 300–800 mg or nizatidine 150-300 mg or famotidine 20–40 mg); premedication with steroids is indicated in subjects who developed a hypersensitivity reaction to ixabepilone in previous cycles. Subjects who are to receive cetuximab are to be premedicated with an H1 antagonist (e.g., 50 mg of diphenhydramine IV)

o. Monitor the subject for hypersensitivity reactions during and after all infusions.

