2.3.1 Cycle 1 Post-Infusion Laboratory Visits

• Perform platelet count and complete blood count with differential at week 1 (+/-3 days) and week 2(+/- 3 days) for the first 4 cycles and thereafter at the expected time of nadir (lowest count of any type of blood cell).

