2.3.2 Cycle 2 Pre-Infusion Laboratory Visit

• Within 72 hours before beginning the Cycle 2 infusion, obtain blood sample for analysis of albumin, alkaline phosphatase, ALT, AST, total bilirubin, blood urea nitrogen, calcium, chloride, creatinine, glucose, lactic dehydrogenase, potassium, phosphorus, and sodium, as well as complete blood count (Hemoglobin, Hematocrit, RBC, WBC, Platelets) with differential (Neutrophils, Lymphocytes, Monocytes, Eosinophils, Basophils). CrCL "CrCl = [(140 - age) x IBW] / (Scr x 72) (x 0.85 for females)" before every cycle for patients with an abnormal creatinine.

• Laboratory tests comprise of calcium, magnesium, and potassium before every dose of cetuximab therapy (before every cycle for the ixabepilone plus cetuximab arm).

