2.3.2.1 Cycle 2 Clinic Visit

• Perform a physical examination to include tumor measurements of the breast and lymph node; record weight and height, karnofsky performance scale, document vital signs. Assess signs and symptoms and document baseline adverse events.

• Subjects who are to receive ixabepilone are to be premedicated approximately

1 hour before the infusion with either 1) both an oral H1 blocker (diphenhydramine 50 mg or equivalent) and an oral H2 blocker (eg, ranitidine 150-300 mg or cimetidine 300–800 mg or nizatidine 150-300 mg or famotidine 20–40 mg); or 2) with premedication per institutional standards. Premedication with steroids is indicated in subjects who developed a hypersensitivity reaction to ixabepilone in previous cycles.

•Subjects who are to receive cetuximab are to be premedicated with an H₁

antagonist (e.g., 50 mg of diphenhydramine IV or equivalent).

 Infuse ixabepilone or ixabepilone plus cetuximab accordingly with the study arm.

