7.0 Treatment Plan/Methods

This is a randomized open-label phase II trial; 116 triple negative breast cancer patients will be randomized equally between 1) Ixabepilone or 2) Ixabepilone plus Cetuximab. The study population will include patients≥ 18 years of age diagnosed with invasive mammary carcinoma. Patients will be assigned to treatment arms using a stratified blocked randomization, with strata based on disease stage (T1N1-3M0 or T2-4 N0-3M0). All patients will receive a physical assessment, imaging, a blood draw, and a core needle biopsy (CNB) a biopsy prior to the start of treatment.

7.1 Treatment Arm 1

Patients will receive Ixabepilone 40mg/m² given over approximately 3-hours on day 1 Patients will receive a total of four cycles of this combination with each cycle given 21(+/- 3) days.

Subjects will be premedicated approximately 1 hour before the ixabepilone infusion with either 1) both an oral H1 blocker (diphenhydramine 50 mg or equivalent) and an oral H2 blocker (e.g., ranitidine 150 300 mg or cimetidine 300–800 mg or nizatidine 150-300 mg or famotidine 20–40 mg); or 2) with premedication per institutional standards. Premedication with steroids is indicated in subjects who developed a hypersensitivity reaction to ixabepilone in previous cycles. Patients with severe reaction should not be retreated (see dose modification chart below).

7.2 Treatment Arm 2

Patients will receive Ixabepilone 40mg/m^2 given over approximately 3-hours on day 1 followed by Cetuximab given on day 1 at 400 mg/m² as an initial loading dose (first infusion) administered as a 120-minute IV infusion (maximum infusion rate 5 mL/min) followed by 250 mg/m² infused over 60 minutes (maximum infusion rate 5 mL/min) as a subsequent weekly dose. Patients will receive a total of 4 cycles of this combination with each cycle being 21 (+/-3) days.

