c. Excludes Grade 3 fatigue/asthenia and transient arthralgia/myalgia for which no dose reduction is required.

d. Responding patients who have sufficiently recovered from toxicity during previous cycle may be considered for retreatment after dose reduction only after discussion with and agreement by Sponsor (TMHRI).

Toxicity	Ixabepilone
Grade 3:	
Grade 3 Platelets	Decrease 1 dose
with: significant	Level ^{a,b}
bleeding or	
requiring platelet	

Dose Modification - Hematologic Toxicities

transfusion	
Grade 4	
Grade 4 Platelets	Decrease 1 dose
	Level ^{a,b}
Grade 4	Decrease 1 dose
Neutrophils lasting	Level ^{a,c}
≥⊡7 days	
Febrile Neutropenia	Decrease 1 dose
any grade	Level ^{a,c}

a. Patients requiring more than 2 dose reductions will discontinue Ixabepilone except those who appear to be benefiting from treatment in which case treatment can be continued after consultation with and approval by the Sponsor (TMHRI)

b. Delay until platelet count ≥□100,000/mm³

c. Delay until neutrophil count $\geq 1,500$ /mm ^{43, 44}

7.3.2. Cetuximab Dose Modifications:

Infusion Reactions

Reduce the infusion rate by 50% for NCI CTC Grade 1 or 2 and non-serious NCI

CTC Grade 3–4 infusion reactions.

Immediately and permanently discontinue cetuximab for serious infusion

reactions, requiring medical intervention and/or hospitalization.45

Dermatologic Toxicity: Recommended dose modifications for severe (NCI-CTC Grade 3 or 4) acneform rash are:

Cetuximab Dose Modification Guidelines for Rash

Severe Acneform	cetuximab	Outcome	cetuximab Dose
Rash Modification			
1st occurrence	Delay infusion 1 to 2 weeks	Improvement	Continue at 250 mg/m ²
		No Improvement	Discontinue cetuximab

2nd occurrence	Delay infusion 1 to 2 weeks	Improvement	Reduce dose to 200 mg/m ²
		No Improvement	Discontinue cetuximab
3rd occurrence	Delay infusion 1 to 2 weeks	Improvement	Reduce dose to 150 mg/m ²
		No Improvement	Discontinue cetuximab
4th occurrence	Discontinue cetuximab		

Patients who experience unacceptable cetuximab toxicity or who are determined to have progressive disease as defined by RECIST during any cycle will be discontinued from the ixabepilone plus cetuximab arm. However if the toxicity is related with cetuximab only; then ixabepilone will be given on a regular basis until the neoadjuvant cycles are completed.

Patients who are deemed not appropriate for further chemotherapy will proceed to local therapy (surgical intervention or radiation therapy).

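### Four visit sections restate the electrolyte check before each weekly cetuximab dose as a check before each cycle, a lower frequency than footnote i and the 72-hour rule require

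*Combined protocol and SAP*

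**What the plan says.** Section 7.2 gives cetuximab to Arm 2 as a loading dose on day 1 and then "as a subsequent weekly dose", for 4 cycles of 21 (+/-3) days. Arm 1 receives none.

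Footnote i, attached to the laboratory row of the flow chart in section 2.0, requires calcium, magnesium and potassium "before every dose of cetuximab therapy and for at least 8 weeks following the completion of cetuximab", and asks that electrolytes be repleted as needed.

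Sections 2.3, 2.3.2, 2.3.3 and 2.3.4 repeat the requirement with an addition: "before every dose of cetuximab therapy (before every cycle for the ixabepilone plus cetuximab arm").

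The week 1 and week 2 laboratory visits (2.3.1, 2.3.2.2, 2.3.3.2, 2.3.4.2) ask for blood counts only. The cycle 1 version reads "Perform platelet count and complete blood count with differential at week 1 (+/-3 days) and week 2(+/- 3 days"). The visit sections mention infusion only at the cycle visits, for example "Infuse ixabepilone or ixabepilone plus cetuximab accordingly with the study arm" in 2.3.2.1.

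A note in section 2.3 says that laboratory analyses must be repeated if the blood was drawn more than 72 hours before ixabepilone or cetuximab is given. It makes an exception for cycle 1, where baseline tests from the preceding two weeks are accepted.

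**The concern.** A nominal 21-day cycle holds three weekly cetuximab doses, so a check before every dose and a check before every cycle are different instructions. The parenthesis cannot refer to another group of patients, because the arm it names is the only arm that receives cetuximab. One sentence therefore gives two frequencies for the same test in the same patients, and it appears four times in the text from which a site would build its visit checklists.

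The stake is patient safety. Section 10.2 reports hypomagnesemia in 55% of cetuximab patients (199/365), severe in 6–17%, with onset from days to months after starting. It can therefore begin between two cycle starts. A check that is not done cannot lead to repletion.

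**Working it through.** The plan states no figure for the number of checks, so there is none to reproduce. The test is a comparison of texts followed by a count.

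**Texts side by side: checks during cetuximab treatment**

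| Place | Frequency of calcium, magnesium, potassium |
|---|---|
| Footnote i, section 2.0 | every cetuximab dose |
| 2.3, 2.3.2, 2.3.3, 2.3.4, main clause | every cetuximab dose |
| Same four sections, parenthesis | every cycle |
| 72-hour note, section 2.3 | repeat if the sample is over 72 hours old at ixabepilone or cetuximab administration |
| 2.3.1, 2.3.2.2, 2.3.3.2, 2.3.4.2 | not listed (blood counts only) |
| 2.7.1 | chemistry panel before each chemotherapy cycle; more often if medically indicated |

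Sections 2.4 and 2.6 add monitoring for at least 8 weeks after cetuximab ends, but nothing between weekly doses. A sample drawn on or before day 1 is at least 7 days old at the second weekly dose, which exceeds 72 hours. On its plain words the 72-hour note would require a repeat there, so the parenthesis conflicts with that note as well as with footnote i.

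**Count per Arm 2 patient** (inputs from section 7.2: 4 cycles, 21 days, weekly doses)

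- Doses: 4 × 21 / 7 = 12. The protocol does not state this number; it assumes 21-day cycles without delay.
- Checks under footnote i: 12.
- Checks under the parenthesis: 4 × 1 = 4.
- Difference: 12 − 4 = 8, and 8/12 = 67%.
- If k of the 4 cycles are run on the parenthesis, 2k checks are missed: 0, 2, 4, 6 or 8 of 12 (0%, 17%, 33%, 50%, 67%).

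**Longest gap between checks**

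- Per dose: 7 days.
- Per cycle: 21 days nominally, and 21 + 3 = 24 days at the edge of the window in section 7.2. The study summary gives Arm 2 a window of +/-2 days, which would make it 23.

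**Sensitivity to missed doses.** For severe rash, section 7.3.2 says "Delay infusion 1 to 2 weeks". If such a delay drops one mid-cycle dose (an assumption), the ceiling is 11 − 4 = 7 of 11 (64%). If it drops two, it is 10 − 4 = 6 of 10 (60%). Permanent discontinuation of cetuximab lowers the number of missed checks further.

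**The case against.** The strongest reply is that the requirement was never dropped. All four sentences keep the words about every dose, footnote i is part of the section 2 schedule, and the 72-hour note names cetuximab. The note sits in the cycle 1 section, but its exception for cycle 1 makes sense only if it also reaches later cycles. All of this stands. A reader might infer that the plan provides for no mid-cycle electrolyte check at all, and the documents do not support that. The note still does not name the electrolytes at the weekly doses, and its exception may weaken it in cycle 1.

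A reader might also take the flow chart's single on-treatment laboratory column, "Prior to Each Cycle", as proof of a gap. It is not. Footnote i hangs on that row, and footnote h schedules the week 1 and week 2 blood counts in the same way, without a column of their own.

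A third reply is that the parenthesis only says what to add for Arm 2 at the pre-cycle draw, since the routine panel for cycles 2 to 4 omits magnesium ("glucose, lactic dehydrogenase, potassium, phosphorus, and sodium, as well as complete blood count"). That may be how it arose. It is not needed for that purpose, because each cycle's day 1 treatment includes a cetuximab dose. Redundant wording would be harmless, but this wording states a different frequency.

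Finally, section 10.2 itself asks only for periodic monitoring, and a per-cycle check plus the follow-up after treatment would arguably meet that. This limits the seriousness. It does not remove the conflict, because the protocol chose the stricter rule in footnote i.

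**Conclusion.** The point holds as a self-contradictory safety instruction. Four sections carry the lower frequency, and no visit section lists the check before the second and third weekly dose of a cycle. Followed literally in every cycle, the parenthesis gives 4 of 12 nominal checks, up to 24 days apart.

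This is a hypothetical ceiling. It assumes undelayed 21-day cycles for the count, the full +3 day window for the gap, and staff who set aside the main clause, footnote i and the 72-hour note throughout. A reader might infer that checks will in fact be missed or patients harmed; the documents give no basis for either number. It is a minor patient-safety correction. The pCR analysis, power and type I error are unaffected.

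**What to change.** Delete the parenthesis about every cycle in 2.3, 2.3.2, 2.3.3 and 2.3.4, so that the main clause stands alone and agrees with footnote i.

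In 2.3.1, 2.3.2.2, 2.3.3.2 and 2.3.4.2 add: *Arm 2 only: calcium, magnesium and potassium before each weekly cetuximab dose (footnote i), sampled within 72 hours before the dose (72-hour rule, section 2.3).* The two sources are cited separately because footnote i states no time window. Leave the +/-3 day window for the blood counts as it is.

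The cost is wording in eight short sections. The visit text would list two more electrolyte panels per cycle, at most 2 × 4 = 8 per Arm 2 patient on the nominal schedule, all of which footnote i already requires. A separate sample may be needed when the week 1 or week 2 blood count is not drawn before the dose.
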